4.4.2 Secondary outcome variables

Both serum cortisol levels will only be measured in patients not receiving exogenous corticosteroids.

Independent variables

- **Basal serum cortisol level** (quantitative continuous)
 - Measured \pm 2 hours from the start of opioid weaning
- **Weaning serum cortisol level** (quantitative continuous)
 - Measured on the day of transfer to ward or after a maximum of 72 hours after start of weaning, at the same time of day as the first measure, whichever occurs first.
- **Change in serum cortisol levels** (quantitative continuous)
 - Difference between weaning and basal serum cortisol levels

Confounding variables

- **Timing of sample in hh:mm** (quantitative continuous)
 - Cortisol is secreted in a diurnal pattern (53)
 - Serum cortisol samples will be taken at the same time of day
- **Presence of primary adrenal insufficiency** (qualitative nominal - dichotomous)
 - According to past medical history in medical chart
 - Patients with this condition may present with hypocortisolemia and receive exogenous corticosteroids, which may confound serum cortisol assays
- **Presence of acute illness** (infection, trauma, surgery, illness) (qualitative nominal)
 - According to APACHE II score at ICU admission
 - Cortisol has been studied as a marker of severity of disease, with higher levels associated with worse prognosis. This association appears to be stronger during the first two days of admission (54)
 - May thus increase cortisol levels depending on severity of disease (53)

- May also provoke transient adrenal insufficiency (53)
- **Presence of septicemia or septic shock** (qualitative nominal - dichotomous)
 - Diagnosis of sepsis will be noted according to medical chart
 - Sepsis causes relative adrenal insufficiency in up to 30 to 70% of patients, which may confound results (55-57)
- **Medications (ketoconazole, spironolactone, dopamine agonists, etc.)** (qualitative nominal)
 - May reduce cortisol production (53)

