5.1.2 Statistical inference

To gauge for presence of evaluation bias, inter-rater agreement will be determined using Cohen's kappa. This test measures the extent to which physicians concur when assessing for presence of OIWS using the DSM-5 criteria. A kappa of ≥ 0.61 is indicative of good inter-rater agreement (70).

For secondary outcomes, baseline, weaning and change in cortisol levels will be compared between patients positive and negative for OIWS. A Student's t-test or a Wilcoxon signed rank test will be used. The test will be determined based on distribution and sample size.

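### The between-group comparisons of basal and weaning cortisol levels mix clock hours, and sample time and sepsis are recorded as confounders but not used in the analysis

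*Combined protocol and SAP*

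**What the plan says.** Section 4.4.2 sets the sampling. The basal sample is taken within "2 hours from the start of opioid weaning". The weaning sample is taken on the day of ward transfer or at most 72 hours after the wean began, "at the same time of day as the first measure". Patients receiving exogenous corticosteroids are not sampled.

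The same section lists confounders for cortisol. One is "Timing of sample in hh:mm", with the reason that "Cortisol is secreted in a diurnal pattern" and the statement "Serum cortisol samples will be taken at the same time of day". Another is septicemia or septic shock: "Sepsis causes relative adrenal insufficiency in up to 30 to 70% of patients", and "Diagnosis of sepsis will be noted according to medical chart". Primary adrenal insufficiency, acute illness and certain drugs are listed as well.

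Section 5.1.2 states the analysis: "baseline, weaning and change in cortisol levels will be compared between patients positive and negative for OIWS", by a t-test or a Wilcoxon test chosen on distribution and sample size. No covariate, stratum, restriction or sensitivity analysis for sample time or sepsis appears in 5.1.1, 5.1.2 or 6.2. The secondary objective in Section 3 asks whether OIWS goes with a rise in serum cortisol.

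**The concern.** A wean can start at any hour, since the definition in 4.3.1 has no clock restriction. The 10am to 2pm window in 4.5 governs the daily evaluations, not the cortisol draw. Two patients' basal samples can therefore be many hours apart on the clock, and so can their weaning samples. Matching the second draw to the first removes a stable clock effect from the within-patient difference. It does nothing for a basal or weaning level compared across patients.

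Two of the three planned comparisons thus carry variation that the plan itself identifies and records. Sepsis is in the same position and reaches all three. A constant shift in level due to sepsis cancels in the change, but an impaired cortisol response does not, nor does sepsis that starts or resolves between the samples. At stake is the sensitivity of an exploratory biomarker comparison in a small study and, if the groups happen to differ in hour or sepsis, a difference wrongly attributed to withdrawal.

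**Working it through.** **No plan figure to reproduce.** The target of 50 patients (5.2) rests on feasibility, and the plan gives no cortisol SD, effect size or power.

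**Step 1: what is matched.** The basal hour is the patient's own wean start, give or take 2 hours. The weaning hour equals that patient's basal hour. Clock hour is therefore matched within a patient and free between patients. Section 4.5 repeats the sampling rule without the same-hour condition, so the match rests on 4.4.2 alone.

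**Step 2: noise in a level.** Assume level = mean + a·cos(2π(h − peak)/24) + residual, with residual SD 1 (the same-hour SD) and h uniform over 24 hours. The variance of the cosine term is a²/2, so total variance = 1 + a²/2 and the effective sample fraction = 1/(1 + a²/2).

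For power, take 50 × 0.167 = 8.35, about 8 OIWS-positive and 42 negative (16.7% is the adult incidence quoted in Section 1), with a true difference of 1 same-hour SD and two-sided 0.05. Then √(1/8 + 1/42) = 0.386, and power = Φ(1/(0.386·√(1 + a²/2)) − 1.96).

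| a (assumed) | Variance | Effective sample | Power |
|---|---|---|---|
| 0 | 1.000 | 100% | 74% |
| 0.5 | 1.125 | 89% | 69% |
| 1 | 1.500 | 67% | 56% |

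The change does not carry this term if both samples are taken at the same hour and the diurnal pattern is stable.

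**Step 3: bias, only if hours differ.** With the same mean hour pattern in both groups, the simulated false-positive rate of the unadjusted t-test stays at about 5%. As an illustration of imbalance, assume peak 08h, OIWS-negative draws uniform over 08–16h and OIWS-positive draws 2 hours later (10–18h). The mean cosine over 08–16h is (24/(2π·8))·(sin 120° − sin 0°) = 0.477 × 0.866 = 0.41. Over 10–18h it is 0.477 × (sin 150° − sin 30°) = 0. The spurious difference is 0.41a: 0.21 SD at a = 0.5 and 0.41 SD at a = 1. Simulated false-positive rates (8 v 42, 20,000 runs) are 8.2% and 16.5%.

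**Step 4: sepsis, only if prevalence differs.** Assume sepsis shifts the compared measure by 0.5 to 1 SD and prevalence differs by 20 points (30% v 50%). Bias = 0.20 × 0.5 to 0.20 × 1 = 0.10 to 0.20 SD, with simulated false-positive rates of about 6% to 8%. At equal prevalence the rate stays near 5%.

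The amplitudes, peak hour, hour shift, sepsis effects and prevalences in steps 2 to 4 are assumptions, because the documents give none.

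**The case against.** The strongest reply has four parts.

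- **Timing is handled by design.** The plan says "Serum cortisol samples will be taken at the same time of day". A reader might take this as one common hour for all patients. The documents do not support that reading: the basal draw follows a clinical event within a 2-hour window, the second is matched to the first, and recording the time as a confounder would serve little purpose if everyone shared one hour. If a common hour is meant, it conflicts with the window and the two statements must be reconciled.
- **The stated objective is already protected.** This stands for clock hour. The objective concerns a rise, which is the change, and the change is sampled at the same hour. It does not stand for sepsis.
- **The plan limits its own claims.** Section 6.1 calls the cortisol work exploratory, and 6.2 concedes confounding, disclaims significant associations and describes the analyses as mainly descriptive. That lowers the weight of the point. It does not answer it, because 5.1.2 still tests all three measures and a general concession does not deal with two named, recorded variables. Section 5.1.1 compares clinical characteristics by OIWS status, but does not name sample hour or sepsis.
- **Very few OIWS-positive patients will remain after exclusions.** This stands, and it limits what the sensitivity analysis can show.

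Stronger readings are tempting. One is that the level comparisons are biased. Nothing in the documents links wean hour or sepsis to OIWS status. A spurious difference of about 0.65 SD can be produced at a = 0.5, but only by putting all OIWS-positive draws at 08–12h and all negative draws at 14–18h, windows that do not overlap. Another is that sepsis dilutes the mean rise by 12% to 28% (0.40 × 0.30 to 0.40 × 0.70). That ignores the words 'up to' in the plan's figure, treats relative insufficiency as no rise at all, assumes a 40% septic share, and overlooks that patients on corticosteroids are not sampled.

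**Conclusion.** The point holds as an inexpensive improvement to a secondary, exploratory analysis. The plan names and records sample hour and sepsis as cortisol confounders, then compares groups without using either.

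For the two level comparisons the cost is lost precision wherever wean hours vary: 12.5% to 50% more variance for an assumed swing of 0.5 to 1 same-hour SD with weans spread over the day, and less if weans cluster in part of the day. Bias is possible, not shown; it needs a difference in hour or sepsis between the OIWS groups. The change is free of a stable clock effect provided that the same-hour rule in 4.4.2 is followed, but it remains open to sepsis. The main aim of describing signs and symptoms is not affected.

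**What to change.** In 5.1.2:

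1. Make the change in cortisol the single inferential comparison between OIWS-positive and OIWS-negative patients, since it matches the secondary objective.
2. Report basal and weaning levels descriptively, with sample hour and sepsis status tabulated by OIWS group so that any imbalance can be seen.
3. Add one sensitivity analysis of the change that leaves out patients with sepsis, adrenal insufficiency or the cortisol-lowering drugs listed in 4.4.2, labelled exploratory.

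Repeating the same-hour condition in 4.5 would secure the match on which item 1 depends.

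The cost is analysis-plan wording, one table and one extra analysis from data already being collected. Two formal tests are given up. The sensitivity analysis will be thin: about 8 of 50 patients would be OIWS-positive before any exclusion, and if 20% to 40% of them were septic (assumption), 8 × 0.8 = 6.4 to 8 × 0.6 = 4.8 would remain, before the corticosteroid restriction and the other exclusions. It can show whether the direction of the result is stable, and little more. For the same reason a model adjusting for many covariates is not proposed.

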4.5 Data collection and study procedure (Appendix II)

From February to October 2018, patients from the MGH and RVH critical care units will be screened daily from unit patient lists generated through Oasis for eligibility. The investigators will be transiting daily between both centers. Once a patient is approaching 72 hours of mechanical ventilation and regular opioid administration, subjects will be evaluated for inclusion and exclusion criteria according to medical chart, and data will be recorded in the "Patient Screen Log". Once a patient fits our entry criteria, here are the steps for obtaining consent:

1- A member of the treating team (ICU physician or patient nurse) will inform the patient about this research project. If the patient is deemed unfit to provide informed consent, the patient's decision maker will be approached.

2- If patient/decision maker shows interest, a member of the research team, independent of the clinical care of the patient will meet with the patient/decision maker and explain the research and seek informed consent.

3- If the intubated patient verbally agrees but is unable to sign the consent, then a witness will sign the consent and the discussion will be documented on the consent form.

4- If the consent is obtained from a decision maker, then we will further seek direct patient consent as soon as patient is deemed apt to consent.

In this case, we would ask the patient to sign a new consent form and a copy will be provided to the patient and the newly signed consent will be kept in our files.

Once recruitment is completed, the patient will be given a subject number and placed on the "Enrollment List", which includes medical record numbers, admission dates, screen dates and enrollment dates.

After enrollment, demographic, reason for admission, lifestyle and medical data will be collected retrospectively from the medical chart, the patient's family and the medical team, and will be noted in the "Enrollment and Outcomes Form". The reasons for exclusion and the number of patients who refused consent will be collected. Temporarily excluded patients will be re-evaluated daily for possible inclusion into the study.

Once the patient begins the targeted opioid weaning of $\geq 10\%$, investigators will perform evaluations daily between 10am and 2pm. These evaluations will consist of using pre-tested data collection sheets to record signs and symptoms of possible OIWS, opioid doses, administered medications, laboratory values and other clinical data such as the RASS, CPOT and CAM-ICU scores. Data collection will be based on subject observation and interview when possible, nurse assessments, medical charts and laboratory results. Serum cortisol levels will be measured on the first day of opioid weaning (± 2 hours from dose decrease) and on the day patient is transferred to the ward or 72 hours from start of weaning whichever occurs first.

Once a weaning episode is identified, the physician collaborator will be contacted to perform daily DSM-5 evaluations. DSM-5 evaluations will be placed in opaque envelopes and investigators will be blinded to the results throughout the study. Additionally, for each patient, at least one inter-rater DSM-5 evaluation between 2 physician collaborators will be performed in order to assess interrater reliability. The two evaluations will be done within 2 hours of each other to minimize time-related discrepancies.

If opioid weaning is unsuccessful and opioid dose is re-increased, the subject will continue to be observed, however daily evaluations will only resume at the next weaning episode. Daily follow-up ends on day of transfer to the ward. One additional data collection and DSM-5 evaluation will be performed on the same day within 24 to 96 hours following transfer. Follow up ends 14 days after initial opioid weaning if patient remains in the ICU or if patient dies.

4.6 Measurement tools

DSM-5 (Appendix IV)	
 - No validated diagnostic tools for OIWS currently exist in the adult ICU - DSM-5 is the gold standard for diagnosing opioid withdrawal in numerous settings - Although not validated in the ICU population, it remains the most appropriate OIWS diagnostic tool for the study (9, 58)
APACHE II score (Appendix V)	
 - Validated tool to predict the risk of mortality in ICU patients (47, 59) - Calculated by an archivist using data collected in the first 24h of ICU admission - In this study: to assess patient disease severity at enrollment
Glasgow Coma Scale (GCS) (Appendix VI)	
 - Validated in ICU and trauma patients to assess the severity of head trauma based on ocular, verbal and motor criteria (48) - GCS score ≤ 8: comatose patient with no evidence of eye or verbal response - GCS score 9-15: presence of eye and verbal response (60) - In this study: to assess the level of consciousness of trauma patients and to verify exclusion criteria at ICU admission
Child-Turcotte-Pugh score (Appendix VII)	
 - Extensively studied in critically ill patients to assess liver function (61) - In the ICU, CTP scores at admission correlate with 12-month mortality (62) - In this study: to assess severity of hepatic dysfunction at ICU admission
Confusion Assessment Method (CAM) (Appendix IX)	
 - Validated tool to identify delirium in patients on general medicine hospital wards - Enables non-psychiatrist clinicians to quickly determine if delirium is present (63) - In this study: performed by the investigator within 24-96 hours of ICU transfer to ward
CAM-ICU (Appendix VIII)	
 - Validated tool to identify presence of delirium in a dichotomous manner in the ICU (64) - In this study: collected daily by investigators or according to nurse assessment
Richmond Agitation Assessment Scale (RASS) (Appendix X)	
 - To assess level of agitation and sedation, and to prevent under or over sedation in ICU - Scale ranges from -5 (unarousable sedation) to +4 (combative) - RASS score ≤ -3 indicates a deeply sedated state (65) - In this study: collected daily by investigator and according to nurse assessment - RASS + 1 defines restlessness and RASS ≥ 2 defines agitation
Agitated Behaviour Scale (ABS) (Appendix XI)	
 - Originally designed to assess agitation in patients with traumatic brain injury (66) - Validated in numerous settings, including long-term care facility (67) - ABS score ≥ 22: Agitation, ≤ 21: No agitation (68) - In this study: performed once by the investigator within 24-96h of ICU transfer
Critical-Care Pain Observation Tool (CPOT) (Appendix XII)	
 - To assess pain in critically ill mechanically ventilated patients based on facial expressions, body movements and muscle tension during nociceptive procedures - To qualify pain in patients unable to verbalize; in patients able to communicate, self-reporting of pain remains the gold standard - CPOT > 2: unacceptably high level of pain, ≤ 2: minimal to no pain (68) - In this study: measured daily by investigators and according to nurse assessment
Numeric Rating	
 - To assess pain intensity on a numerical scale, most commonly ranging from 0 to 10

Scale (NRS) (Appendix XIII)	(NRS-11); only the scale extremities are detailed (69) - In this study: to assess pain during daily evaluations once patients can self-report. Investigators will ask patients to rate their pain on a scale from 0 (absence of pain) to 10 (worst pain imaginable). An NRS ≥ 4 represents an unacceptable level of pain.
---------------------------------------	---

5. Data analysis

5.1 Statistical analysis

5.1.1 Descriptive statistics

Demographic and clinical characteristics of patients who developed OIWS will be compared to those who did not. Categorical variables will be presented as proportions. For continuous variables, means and standard deviations will be computed for normal distributions whereas medians (interquartile range) will be used for non-normal distributions.

For the primary outcome, episodes will be compared between the withdrawal positive (W+) group and the withdrawal negative (W-) group. Every day on which the DSM-5 is positive is equivalent to an episode of withdrawal, whereas a negative DSM-5 counts as an episode in which no withdrawal was observed. Patients who are positive for at least one episode of withdrawal make up the W+ group, whereas those who did not have a single episode of withdrawal make up the W- group, thus eliminating crossover. If a single patient experiences multiple days of withdrawal, s/he will account for multiple episodes in the study. Signs and symptoms will be tallied per episode and compared between the two groups. The results will be presented as proportions (i.e. incidence of symptom per total episodes). In the event of a discordant inter-rater evaluation, only the positive result will be taken into account.

For the secondary outcome, serum cortisol levels and changes in serum cortisol levels are continuous variables and therefore descriptive statistics will be used as stated above, depending on the distribution.

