Appendix XII. Critical-Care Pain Observation Tool (CPOT) developed by Gelinas et al. .35
Appendix XIII. Numeric Rating Scale (NRS).....36

Abbreviation list

ICU	Intensive care unit
IWS	Iatrogenic withdrawal syndrome
MGH	Montreal General Hospital
MUHC	McGill University Health Centre
OIWS	Opioid-associated iatrogenic withdrawal syndrome
PICU	Pediatric intensive care unit
RVH	Royal Victoria Hospital

1. Introduction

Adult medical, surgical and trauma intensive care unit (ICU) patients routinely experience pain, agitation, delirium and anxiety (1). Opioids and benzodiazepines are the primary medications to relieve pain, facilitate mechanical ventilation and decrease physiological and psychological stress in the critically ill (1). In a prospective, observational study in 51 Canadian ICUs, 92% of patients received opioids and sedatives at least once during mechanical ventilation (2). Upon repeated and prolonged administration, opioid tolerance may develop as a result of receptor desensitization and upregulation of excitatory intracellular pathways (2, 3). When these drugs are abruptly discontinued or rapidly tapered, patients may develop a cluster of signs and symptoms known as the acute iatrogenic withdrawal syndrome (IWS). While this phenomenon is well described in the pediatric critical care population, there is a paucity of data in critically ill adults (4-7). IWS has been associated with negative clinical outcomes such as increased length of hospital stays, prolonged duration of mechanical ventilation and higher cost of hospitalization (4-7).

In one prospective, observational study, the reported incidence of IWS in the adult ICU population was 16.7% (8). In prospective studies done in the pediatric ICU (PICU), observed incidence was 7.5 to 100% (9). Two assessment tools have been validated in children: The Withdrawal Assessment Tool-Version 1 (WAT-1) and the Sophia Observation Withdrawal Symptoms-scale (SOS) (10). No such tool currently exists in the adult ICU (9).

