Opioid withdrawal appears to present differently in adults (4). In a prospective study evaluating the validity of the WAT-1 in the adult ICU, commonly observed symptoms in the PICU such as diarrhea, vomiting and fever did not correlate with a diagnosis of IWS (8, 22). Chiu et al. reports that withdrawal symptoms in adults tend to begin with anxiety, irritability, agitation and dysphoria, followed by sweating, rhinorrhea, tachypnea, insomnia and yawning in the acute phase. Symptoms such as mydriasis, tachycardia, hypertension, nausea, vomiting, piloerection and fever manifest during subsequent phases of withdrawal (4). In the retrospective study by Cammarano et al., IWS was diagnosed using a modified Himmelsbach scale, which assesses the severity of opioid withdrawal in chronic users only (7, 23). Thus, the symptoms identified in this study may not be applicable to opioid-naïve patients. It is currently unclear whether all these symptoms can be identified in opioid-naïve critically ill patients.

The distinction between opioid and benzodiazepine withdrawal remains unclear because both drugs are often used simultaneously in the ICU setting. Duceppe et al. reports that there are currently no adult or pediatric ICU studies that evaluated the incidence of isolated opioid or benzodiazepine withdrawal symptoms (9). The 2002 adult critical care guidelines, updated in 2013, identifies nausea, vomiting, sweating, agitation, restlessness, irritability, anxiety and muscle cramps as common symptoms to both acute opioid and benzodiazepine withdrawal (1, 18). Benzodiazepine and opioid withdrawal symptoms largely overlap, which contributes to the difficulty in describing both syndromes adequately (20, 24).

Assessment tools

As stated previously, in the PICU, two validated tools are commonly used to assess IWS: the WAT-1 and the SOS. Both are included in the 2016 European clinical guidelines for pain, sedation, withdrawal and delirium assessment in critically ill infants and children (10). However, they were validated in a manner that could potentially affect the results' reliability – in the psychometric evaluation studies, the same nurse scored both the tool and withdrawal severity. The lack of blinding to the presence of IWS and the lack of independent evaluation thus make those studies susceptible to observer bias. The WAT-1 performed poorly in the adult ICU, suggesting that the presentation of IWS is different in adults as compared to children (4).

Biomarkers

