5.2 Sample size

Based on our experience with the WAAICUP studies, 88 patients were eligible to participate in the study in an 8-month period, of which around 50 consented (22). We thus aim to recruit 50 patients based on the feasibility of these previous studies.

6. Advantages and limitations

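### The primary sign table counts only patient-days: a few long-course patients can dominate it, and the order of signs can differ from the per-patient order, so patient-level columns should be added

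*Combined protocol and SAP*

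**What the plan says.** Section 5.1.1 sets the unit of the primary outcome: "Every day on which the DSM-5 is positive is equivalent to an episode of withdrawal", and a negative DSM-5 day counts as an episode without withdrawal. Repeated days all count: "If a single patient experiences multiple days of withdrawal, s/he will account for multiple episodes in the study". The summary measure is then fixed: "The results will be presented as proportions (i.e. incidence of symptom per total episodes". The groups, however, are defined by patient: "Patients who are positive for at least one episode of withdrawal make up the W+ group".

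Section 5.1 plans no per-patient proportion, no count of patients with each sign, no report of days per patient and no interval that treats the patient as a cluster. The inference in 5.1.2 covers only kappa and cortisol. The limitations in 6.2 do not mention repeated days.

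Under 4.5, evaluations are daily until ward transfer, with one more on the ward, and follow-up in the ICU stops at 14 days. Daily evaluations pause when the opioid dose is re-increased. The number of days a patient contributes will therefore vary, and partly for reasons other than withdrawal.

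**The concern.** The primary objective is to identify the signs of OIWS, and this table is the whole primary result. With patient-days as the only unit, a patient with ten counted days weighs ten times a patient with one. The result answers how often a sign is present on a counted day. It does not answer how many patients with OIWS show it.

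The documents give reasons to expect the two answers to differ:

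- The Clinical presentation part of section 2 describes signs that come in phases: "Symptoms such as mydriasis, tachycardia, hypertension, nausea, vomiting, piloerection and fever manifest during subsequent phases of withdrawal". A brief sign shown by every W+ patient is diluted as courses lengthen.
- Section 4.4.1 notes that withdrawal has been associated with longer ICU stays, so the weights may be related to the condition itself.
- Section 4.4.1 also lists other causes of signs that can persist over days in one patient, such as fever from infection or diarrhea from enteral feeds.

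At stake is which signs are carried forward to the screening tool named in 4.1, and how much evidence a reader believes lies behind each proportion.

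**Working it through.** **Plan's own figure.** There is no power calculation to reproduce. Section 5.2 rests on feasibility: "88 patients were eligible to participate in the study in an 8-month period, of which around 50 consented", that is 50/88 = 56.8%, hence the target of 50.

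**Number of W+ patients.** The Introduction gives one prospective adult figure: "the reported incidence of IWS in the adult ICU population was 16.7" percent. Expected W+ = 50 × 0.167 = 8.35. Binomial spread: 5 or fewer with probability 0.14, 13 or more with probability 0.06. Section 2 also cites 19.7 to 100% from retrospective studies. At 19.7%, 50 × 0.197 = 9.85. At 26% and 40%, 50 × 0.26 = 13 and 50 × 0.40 = 20.

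**Assumptions.** The documents give no course lengths and no within-patient correlations, so all of those below are assumed. The examples count only positive days of W+ patients, which 5.1.1 does not settle.

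**Example 1.** Eight W+ patients with 1, 2, 2, 3, 3, 4, 6 and 10 days (31 days).

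- Sign on all days of the 10-day patient only: per day 10/31 = 32.3%; patients 1/8; equal-weight mean 1/8 = 12.5%.
- Sign on day 1 only, in all eight: per day 8/31 = 25.8%; patients 8/8; equal-weight mean (1 + 1/2 + 1/2 + 1/3 + 1/3 + 1/4 + 1/6 + 1/10)/8 = 3.183/8 = 39.8%.

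**Example 2.** Sign A is on every day of the three longest courses, sign B on every day of the other five. Per patient: A 3/8 = 37.5%, B 5/8 = 62.5%.

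- Days 8, 7, 6, 1, 1, 1, 1, 1: per day A 21/26 = 80.8%, B 5/26 = 19.2%. Reversed.
- Days 3, 3, 2, 2, 2, 1, 1, 1: per day A 8/15 = 53.3%, B 7/15 = 46.7%. Still reversed.
- Two days each: per day A 6/16 = 37.5%, B 10/16 = 62.5%. No difference.

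**How often a few patients hold most of the days.** 40,000 simulations per setting, geometric course lengths capped at 14 days. Percentage of runs in which the longest courses hold more than half of the positive days:

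| W+ patients | Longest courses | Mean 1.5 days | 2 days | 3 days | 5 days |
|---|---|---|---|---|---|
| 8 | three | 63.6 | 87.3 | 96.4 | 98.6 |
| 8 | two | 6.4 | 20.2 | 38.1 | 45.9 |
| 10 | three | 24.2 | 54.2 | 76.7 | 86.0 |
| 13 | three | 2.6 | 13.5 | 32.3 | 38.7 |
| 20 | three | 0.0 | 0.1 | 0.5 | 0.2 |

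**Ranking.** Two signs with true per-patient proportions 0.60 and 0.40, 8 W+ patients.

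- Signs unrelated to course length (correlation 0.3 to 0.6): the two orders disagree in 4 to 13% of runs. The order is wrong in 14 to 20% per day and 15 to 18% per patient.
- Rarer sign goes with longer courses (correlation 0.5, mean 2 to 5 days): the orders disagree in 9 to 18%. The order is wrong in 21 to 29% per day and 16 to 18% per patient.

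**Apparent information.** Design effect = 1 + (Σd²/Σd − 1) × ρ, where d is a patient's number of days and ρ the within-patient correlation. In example 1, Σd² = 179. At ρ = 0.4 it is 1 + (179/31 − 1) × 0.4 = 2.9, so 31 days carry the information of about 31/2.9 = 11 independent ones.

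**The case against.** The strongest defence is that a day-level proportion is a legitimate target. Evaluation is daily, the eventual aim is a bedside tool, and 5.1.1 states its unit openly. That stands: the day-level column should stay. What fails is the label, because a length-weighted day-prevalence is not an incidence. It is also the only column.

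A reader might infer that two or three patients will decide which signs look typical. The documents do not support that. They give no course lengths. Under the assumptions above, two patients do not usually hold most of the days even with 8 W+ patients, and dominance by three fades with 13 to 20.

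A reader might also infer that the planned ranking is simply wrong. It differs from the per-patient ranking, and it does clearly worse on the per-patient question only if signs are related to course length. Otherwise about 8 patients give a noisy order under either unit. The examples are constructed to show what can happen, not what is expected.

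Finally, no test or interval on signs is planned, and 6.2 calls the analyses predominantly descriptive. Clustering therefore invalidates no planned inference and raises no type I error. The issue is weighting and apparent precision. Being descriptive is not a full answer, since readers will then rely on the proportions and denominators alone.

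**Conclusion.** The point holds as a gap in reporting. Section 5.1.1 gives each sign only as a share of patient-days, so long courses weigh more and the day count overstates the evidence. With about 8 W+ patients, which rests on the single 16.7% figure, a few long courses can dominate the table and the order of signs can reverse between units. The size of the effect cannot be fixed from the documents. It depends on course lengths, within-patient correlation, the number of W+ patients, and whether negative days of W+ patients enter the denominator. If they do, weight follows evaluated days and the figures above change, though the mechanism does not.

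This should be fixed but is not critical: the study is descriptive, and the daily data allow the patient-level summaries to be produced later.

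**What to change.** In 5.1.1, keep the per-episode proportion, label it as the proportion of evaluated days with the sign, and state which days of W+ patients enter the denominator. For each sign, in both W+ and W-, add:

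- (a) the equal-weight mean of the per-patient proportions of days with the sign;
- (b) the number and proportion of patients with the sign on at least one counted day, together with the number of evaluated days per patient, because ever showing a sign depends on how often one is looked at;
- (c) if an interval for the W+ minus W- difference is given, compute it with the patient as the cluster, by patient bootstrap or by GEE with a small-sample correction.

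Column (b) is needed as well as (a). A sign confined to day 1 of equal 5-day courses scores 1/5 = 20% under either weighting even if every patient shows it. With about 8 W+ patients the interval in (c) remains approximate and should be described so: in simulation, a nominal 95% patient bootstrap interval for the W+ proportion covered 89 to 91%.

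The cost is some wording and a little analysis work, with no new data. Equal weighting loses slight precision when within-patient correlation is low (simulated SD 0.135 against 0.131 at a correlation of 0.2). It is best settled before the sign results are seen.
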